The Effect of Combining Spinal Manipulation and Dry Needling in  
Individuals with Non-specific Low Back Pain

Study Protocol and Statistical Analysis Plan

Approved until 12/10/2023

This study will use a randomized comparative design with three intervention groups in individuals with nonspecific LBP. The first patient-reported outcome to be assessed is disability, assessed with the LBP Oswestry Disability Index Questionnaire (ODI). The ODI score is derived from the Oswestry Disability Questionnaire, resulting in a score ranging from 0-100 with higher numbers indicating a greater level of disability [84]. Patient-centered outcome measures represent the majority of clinical nonmechanistic measures from the view and disability outlook of the patient. They are an effective way for the patient to explain the degree of pain and disability being experienced from LBP.

The second patient-reported outcome will utilize the pain rating score derived from the numeric pain rating scale (NPRS) to evaluate pain intensity throughout the trial. Participants will be asked to make separate ratings of current pain intensity and the best and worst intensity over the past 24 hours on a 0-10 scale (“0” no pain and “10” worst imaginable pain). The mean of the three ratings will be used to represent pain intensity.

The mechanistic outcome measures include LMM, ES, and GM muscle activation measured by changes in contraction thickness at rest and sub-maximal isometric contraction. The primary comparison will consist of the combination group compared against each single treatment group of SMT or DN in order to evaluate the advantage of utilizing both modalities together. This study will further perform a secondary exploratory comparison of the SMT and DN only groups. The primary comparison time-point will evaluate these outcome measures at 4-weeks (late effect) compared to baseline and a secondary comparison (early effect) at 2-weeks with comparison being controlled for baseline value. A third comparison time-point will be evaluated at 1-week consisting of

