#### *Statistical methods*

The study treatments will include spinal manipulation therapy (SMT), dry needling (DN), and exercise (EXER). Participants will be block randomized in sizes of 3 and 6 into three study groups: (SMT+EXER), (DN+EXER), and (SMT+DN+EXER). Repeated measurements of the outcomes will be collected at baseline, two weeks post-treatment, and four weeks post-treatment. The first primary outcome is the continuous variable Oswestry Disability Index (ODI). The second primary outcome is the continuous variable 0-10 numeric pain rating scale (NPRS). The primary time point is at four weeks (late effect) and the secondary time point is at two weeks (early effect). To determine if (SMT+DN+EXER) is superior to (SMT+EXER) on the ODI outcome, a linear regression model will be fitted using the 2-week ODI as the outcome variable, group as the primary predictor [(SMT+DN+EXER) vs (SMT+EXER)], and baseline ODI as a covariate, in an analysis of covariance (ANCOVA) fashion. In a similar model, (SMT+DN+EXER) will be compared to (DN+EXER). All comparisons will be made at the alpha 0.05 level.

Exercise compliance will be measured by participants self-reporting adherence to the program by selecting average number of days per week the exercises were completed. Self-reporting will take place during the final visit at the end of the fourth week. Participants will be informed of this method of self-reporting compliance in order to aid in tracking adherence over the two-week period.

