#### *Sample size justification*

For a simple comparison of a post (week 2) standardized (z-score) outcome variable, which is the standardized outcome variable in the ANCOVA model, mean +/- SD: 0 +/- 1 versus 0.64 +/- 1 (that is, a 0.64 SD difference), we required n= 41 per group to achieve 80% power using a two-sided alpha 0.05 comparison. We assumed a

correlation of  $r = .50$  between the baseline and post-treatment outcomes, which was a reasonable assumption given that changes over two weeks would mostly be in the improvement direction, with minimal patients changing in the opposite direction. The  $n=40$  per group sample size was next adjusted to account for the increased power achieved by the ANCOVA approach [180]. In doing this, the  $n = 40$  was multiplied by the factor  $(1 - r^2) = (1-0.50^2) = 0.75$ , so we only required  $n = 40 \times .75 = 30$  per group to achieve the same effect size. Based on prior work of 92% retention to a four-week trial, a sample size of  $n=99$ , 33 per group, accounts for potential participant drop-out [20,168]. This planned sample size works if a 0.64 SD difference is likely or represents at least a minimal clinically meaning difference. In a DN study, baseline ODI was mean  $+\text{- SD } 31.5 \text{ } +\text{- } 11.5$  which decreased to  $23.4 \text{ } +\text{- } 13.5$  one-week post-treatment, a mean difference divided by pooled SD, while assuming  $r=0.50$ , of  $(23.4 - 31.5)/12.6 = -0.64$  SD difference. In the same study, although a difference in NPRS was not reported, baseline NPRS mean  $+\text{- SD}$  was  $5.0 \text{ } +\text{- } 1.7$ . A 0.64 SD improvement would be  $(5.0/1.7) \times 0.64 = 1.9$  point change. This reduction in pain would be noticeable and beneficial to the patient, and so is at least a minimally, clinically relevant effect size [181]. In a SMT study [51,182], reported baseline ODI mean  $+\text{- SD } 32.2 \text{ } +\text{- } 11.9$  which decreased to  $23.9 \pm 11.4$  post-treatment, a  $(23.9-32.2)/11.7 = -0.71$  SD difference. So, both DN and SMT achieve a 0.64 SD effect size by themselves. However, our study specifically tested if DN+SMT is superior to DN and is superior to SMT. Individual participant response to only DN or only SMT could vary, with some level of synergy of DN+SMT being more effective than the sum of the individual effects. Therefore, we used the 0.64

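### Two primary outcomes and two primary contrasts are all tested at 0.05 with no stated success rule; the rule must be written down, and power restated as about 68% for beating both treatments on ODI

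*Combined protocol and SAP*

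**What the plan says.** Statistical methods names two primary outcomes: "The first primary outcome is the continuous variable Oswestry Disability Index (ODI" and, next, "The second primary outcome is the continuous variable 0-10 numeric pain rating scale (NPRS". It writes out a baseline-adjusted regression for ODI comparing the combination with SMT, and adds: "In a similar model, (SMT+DN+EXER) will be compared to (DN+EXER". The opening design description gives the same pair of contrasts, with the aim of showing whether joint use helps: "The primary comparison will consist of the combination group compared against each single treatment group of SMT or DN". It sets the remaining pairwise contrast apart: "This study will further perform a secondary exploratory comparison of the SMT and DN only groups".

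The only statement on significance levels is "All comparisons will be made at the alpha 0.05 level". Sample size justification sizes the trial on one two-sided 0.05 comparison at 80% power. Later in that section the aim is put this way: "our study specifically tested if DN+SMT is superior to DN and is superior to SMT".

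No section says whether one or both contrasts are needed, whether one or both outcomes are needed, or whether NPRS is tested only after ODI.

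**The concern.** Two outcomes times two contrasts make four primary tests, each allowed 0.05. The false-claim rate then depends on a rule that is not written. If one significant result out of four can be reported as primary success, the error rate is well above that of one test. If both contrasts must be won, the error rate is modest, but 80% is no longer the power for the trial's aim, because it describes a single contrast. With nothing written, either reading could be adopted after the results are known.

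**Working it through.** **Inputs from Sample size justification:** effect 0.64 SD, SD 1, baseline-to-follow-up correlation r = 0.50, two-sided 0.05, 80% power, 30 evaluable per arm, 92% retention, 99 enrolled. **From Statistical methods:** separate two-group ANCOVAs. **Assumed:** the ODI-NPRS correlation, which the documents do not give, is varied from 0 to 0.9; the three arms are of equal size.

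**1. The plan's own figure.** For one unadjusted contrast, n = 2 × ((1.960 + 0.842)/0.64)² = 38.3, so 39 by the normal approximation and 40 by the t-test. The plan gives 41, then continues with 40. The ANCOVA factor is 1 − 0.50² = 0.75, and 40 × 0.75 = 30. Then 30/0.92 = 32.6, so 33 per arm and 99 in all. The standard error of an adjusted contrast is √(0.75 × 2/30) = 0.2236, and 0.64/0.2236 = 2.86. Power is Φ(2.86 − 1.96) = 82% by the normal approximation and 80% by the t-test. The stated 80% for one comparison therefore reproduces.

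**2. Dependence between the tests.** Both contrasts use the same combination arm, so their statistics correlate at (1/n)/(2/n) = 0.5. With four independent tests the chance of any false positive would be 1 − 0.95⁴ = 18.5%. The shared arm and the ODI-NPRS correlation bring it down.

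**3. False claims.** These come from simulated ANCOVAs, 30 per arm, with t critical values on 57 df.

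| Rule and true state | Correlation 0 | 0.5 | 0.7 | 0.9 |
|---|---|---|---|---|
| Any of four, two-sided, nothing works | 17.2% | 16.2% | 15.0% | 12.8% |
| Any of four favouring the combination, nothing works | 8.8% | 8.2% | 7.5% | 6.4% |
| Both contrasts on either outcome, nothing works | 0.9% | 0.9% | 0.8% | 0.7% |
| Both contrasts on either outcome, worst case | 4.9% | 4.5% | 4.3% | 3.6% |

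In the worst case the combination equals one single treatment and is much better than the other, on both outcomes. Each outcome then turns on one null contrast at 2.5% in the favourable direction, so at correlation 0 the rate is 1 − 0.975² = 4.9%. At correlation 0.9 a bivariate normal calculation gives 3.5%. If the equal treatment differs by outcome, the range is 4.6-5.0%.

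**4. Power at 30 evaluable per arm and 0.64 SD in every contrast.**

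| Event | Power |
|---|---|
| One contrast | 80% |
| Both contrasts on ODI | 68% |
| Both contrasts on either outcome, unadjusted | 90% (correlation 0), 80% (0.7), 75% (0.9) |
| Holm across outcomes, at least one outcome | 81% (0), 69% (0.7), 64% (0.9) |
| Holm, each outcome | 61-63% |

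The normal approximation puts both contrasts on ODI at 71%; 68% uses the planned ANCOVA and its t critical values.

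**5. NPRS target.** The plan converts 0.64 SD to (5.0/1.7) × 0.64 = 1.9 points. But 0.64 × 1.7 = 1.1 points, and 1.9/1.7 = 1.1 SD. NPRS power cannot be stated until these are reconciled.

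**The case against.** The strongest reply is that the plan already points to a sensible rule. Sample size justification states the aim with an 'and', and the design description seeks the benefit of using the two modalities together. If both contrasts must be won, they need no alpha split, and the false-claim rate stays within the plan's two-sided 0.05 even when success on either outcome counts. It exceeds only a one-direction benchmark of 2.5%, which no section states. All of this stands.

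A reader might therefore infer too much in any of three ways:

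- That the trial has a 13-17% false-positive rate. That holds only if any single result may count. The plan does not exclude this, but its wording points the other way.
- That the four tests need a Bonferroni split. Once both contrasts are required, only the choice between ODI and NPRS remains.
- That the 80% is misstated. It is given for one comparison and is correct for that.

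The reply does not supply the rule. The 'and' describes an aim in a sample size paragraph and names no outcome. Calling the outcomes first and second numbers them without making NPRS conditional on ODI. Only the ODI models are written out, but NPRS is labelled primary and is covered by the blanket 0.05 statement.

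**Conclusion.** The concern holds in a limited form: the success rule is missing, and the one stated rule, 0.05 for everything, does not replace it. The size depends on the reading. Under the better-supported reading the problem is mainly one of wording and power: false claims stay within 0.05, but power for beating both treatments on ODI is about 68%, not 80%. Under the any-one-counts reading, false claims for the combination rise to 6-9%.

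These figures rest on equal arms of 30 evaluable participants and r = 0.50; the power figures also need exactly 0.64 SD in every contrast, and a larger true effect would raise them. Ranges across both outcomes rest on the assumed ODI-NPRS correlation. The design and the sample size arithmetic otherwise stand, so this should be fixed but does not undermine the trial.

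**What to change.** Before group results are seen, replace the sentence "All comparisons will be made at the alpha 0.05 level" with a rule at one named primary time point. (Statistical methods calls four weeks primary but models week 2; that conflict is a separate point.)

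- **Within an outcome:** claim superiority only if both contrasts favour the combination at two-sided 0.05.
- **Across outcomes, either (a)** test ODI first, and NPRS by the same rule only if ODI succeeds; **or (b)** if NPRS must be claimable alone, apply Holm: take the larger of each outcome's two p-values, test the smaller of these at 0.025 and, if it succeeds, the other at 0.05.
- **Everything else**, including SMT versus DN, is secondary with nominal p-values.

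In the worst case of step 3, false claims for the combination are about 2.4-2.5% under (a) and 1.8-2.5% under (b).

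State power as 80% for one comparison and about 68% for beating both treatments on ODI under (a), both at 30 evaluable per arm and 0.64 SD. Add NPRS power only once its target is reconciled.

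No extra patients are needed if the lower power is accepted, but there is a real cost. The chance of any primary claim is 68% under (a) or about 64-81% under (b), against about 75-90% if both contrasts on either outcome counted unadjusted. Under (a) NPRS cannot be claimed if ODI fails. Under both, a win over only one single treatment is not a primary success. For information, 80% power for both ODI contrasts would take 38 evaluable per arm (37 gives 79.5%); 38/0.92 = 41.3, so 42 per arm, or 126 enrolled instead of 99.

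If group results have already been seen, report all four results and disclose that no rule was pre-specified.

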#### *Sample size justification*

For a simple comparison of a post (week 2) standardized (z-score) outcome variable, which is the standardized outcome variable in the ANCOVA model, mean +/- SD: 0 +/- 1 versus 0.64 +/- 1 (that is, a 0.64 SD difference), we required n= 41 per group to achieve 80% power using a two-sided alpha 0.05 comparison. We assumed a

correlation of  $r = .50$  between the baseline and post-treatment outcomes, which was a reasonable assumption given that changes over two weeks would mostly be in the improvement direction, with minimal patients changing in the opposite direction. The  $n=40$  per group sample size was next adjusted to account for the increased power achieved by the ANCOVA approach [180]. In doing this, the  $n = 40$  was multiplied by the factor  $(1 - r^2) = (1-0.50^2) = 0.75$ , so we only required  $n = 40 \times .75 = 30$  per group to achieve the same effect size. Based on prior work of 92% retention to a four-week trial, a sample size of  $n=99$ , 33 per group, accounts for potential participant drop-out [20,168]. This planned sample size works if a 0.64 SD difference is likely or represents at least a minimal clinically meaning difference. In a DN study, baseline ODI was mean  $+\text{- SD } 31.5 \text{ } +\text{- } 11.5$  which decreased to  $23.4 \text{ } +\text{- } 13.5$  one-week post-treatment, a mean difference divided by pooled SD, while assuming  $r=0.50$ , of  $(23.4 - 31.5)/12.6 = -0.64$  SD difference. In the same study, although a difference in NPRS was not reported, baseline NPRS mean  $+\text{- SD}$  was  $5.0 \text{ } +\text{- } 1.7$ . A 0.64 SD improvement would be  $(5.0/1.7) \times 0.64 = 1.9$  point change. This reduction in pain would be noticeable and beneficial to the patient, and so is at least a minimally, clinically relevant effect size [181]. In a SMT study [51,182], reported baseline ODI mean  $+\text{- SD } 32.2 \text{ } +\text{- } 11.9$  which decreased to  $23.9 \pm 11.4$  post-treatment, a  $(23.9-32.2)/11.7 = -0.71$  SD difference. So, both DN and SMT achieve a 0.64 SD effect size by themselves. However, our study specifically tested if DN+SMT is superior to DN and is superior to SMT. Individual participant response to only DN or only SMT could vary, with some level of synergy of DN+SMT being more effective than the sum of the individual effects. Therefore, we used the 0.64

SD effect size for this test as our minimally clinically relevant effect, consistent with the individual treatment effects.

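### The NPRS effect size is miscalculated: 0.64 SD at an SD of 1.7 is about 1.1 points, not 1.9, so the stated case that the trial targets a clinically relevant pain difference fails

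*Combined protocol and SAP*

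**What the plan says.** The Statistical methods section gives pain co-primary status: "The second primary outcome is the continuous variable 0-10 numeric pain rating scale (NPRS".

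The Sample size justification sets the number of participants on a 0.64 SD difference and attaches a condition: "This planned sample size works if a 0.64 SD difference is likely or represents at least a minimal clinically meaning difference". For the NPRS it takes a baseline mean of 5.0 and SD of 1.7 from a dry needling study, and notes that this study did not report an NPRS difference. It then converts 0.64 SD into points with the expression "5.0/1.7) \times 0.64 = 1.9" (the opening bracket comes just before the quoted text). The next sentence draws the clinical conclusion: "This reduction in pain would be noticeable and beneficial to the patient, and so is at least a minimally, clinically relevant effect size". The section closes by adopting 0.64 SD as the smallest clinically relevant effect for the comparisons of the combination with each single treatment.

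**The concern.** A standardised effect is a difference divided by an SD, so the way back to points is to multiply by the SD. The plan instead divides the baseline mean by the SD and multiplies by the effect size. The result has no units and rises with the baseline mean. It also moves the wrong way with the SD: doubling the SD would halve the supposed point change.

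The figure is relied on. With no NPRS difference available from the cited study, the 1.9 points are the only argument that 0.64 SD matters to patients in terms of pain. If the figure is wrong, one of the two primary outcomes has no stated basis for its target. A reader could also take a statistically significant pain result of about 1 point or less as clinically relevant, on the strength of a design said to correspond to 1.9 points.

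**Working it through.** **Inputs, all from the Sample size justification:** effect size 0.64 SD; NPRS baseline mean 5.0 and SD 1.7; two-sided alpha 0.05; power 80%; baseline to post-treatment correlation r = 0.50; retention 92%.

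**1. Reproduce the plan's figure.** 5.0/1.7 = 2.94, and 2.94 x 0.64 = 1.88, which rounds to 1.9. The printed arithmetic is right, so the fault is the formula and not a slip in calculation.

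**2. Correct conversion.** Points = effect size x SD = 0.64 x 1.7 = 1.088, about 1.1 points.

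**3. Size of the error.**
- 1.88/1.088 = 1.73 and 1.9/1.088 = 1.75, an overstatement of 73% to 75%.
- 1 - 1.088/1.9 = 0.43, so the NPRS difference that 0.64 SD represents is 43% smaller than stated.
- As a share of the baseline mean: 1.088/5.0 = 22%, against 1.88/5.0 = 38%.

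**4. Reverse check.** 1.9/1.7 = 1.12 SD, not 0.64 SD. For 1.9 points to equal 0.64 SD, the SD would have to be 1.9/0.64 = 2.97.

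**5. Compare with the plan's handling of the ODI.** The same section divides a difference by an SD: (23.4 - 31.5)/12.6 = -0.64 and (23.9 - 32.2)/11.7 = -0.71. Reversing the first gives 0.64 x 12.6 = 8.1 ODI points, which matches the observed change of 31.5 - 23.4 = 8.1. The NPRS formula applied to that study's baseline ODI would give (31.5/11.5) x 0.64 = 1.75 points for the same 8.1-point change. The two conversions cannot both be right.

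**6. Does n change?** No. On the standardised scale, the noncentral t calculation gives 40 per group (power 0.807 at 40 and 0.817 at 41). Then 40 x (1 - 0.50²) = 30, 30/0.92 = 32.6, rounded up to 33, and 3 x 33 = 99, as planned. No NPRS point value enters this chain.

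**7. Smallest significant NPRS difference.** With 30 analysed per group, SD 1.7 and r = 0.50, the standard error is 1.7 x √0.75 x √(2/30) = 0.38. A difference of about 2.0 x 0.38 = 0.76 points would reach two-sided p < 0.05.

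**8. Sensitivity to the SD.** The 1.7 is a baseline SD. If the follow-up SD were 2.0 or 2.5 (assumed values), 0.64 SD would be 1.3 or 1.6 points. Both are below 1.9.

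**The case against.** The conversion error itself cannot be defended. The case on the other side concerns how much follows from it.

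- *No threshold is given.* The documents cite a source for clinical relevance on the NPRS but state no number, so they do not show that 1.1 points is too small. This stands. The finding is that the argument offered does not support 0.64 SD for pain, not that 0.64 SD is irrelevant.
- *The sample size does not depend on the figure.* It was set on 0.64 SD, and the ODI results of -0.64 and -0.71 are quoted as grounds. This also stands, and n = 99 does not fall with the NPRS figure. But those are ODI figures, and they say nothing about the relevance of a pain difference.
- *The 1.9 points are described as improvement over time, not as a between-group target.* That is a fair reading of the wording. It does not rescue the conversion, and the plan still uses the figure to defend the effect size for a between-group test.
- *A small significant difference is possible after correction too.* True: about 0.76 points would be significant either way. What the error adds is a wrong premise about what the targeted effect means to patients.
- *1.09 is too exact.* In the cited study the ODI SD rose from 11.5 to 13.5. If the NPRS SD rose in proportion (an assumption), it would be 1.7 x 13.5/11.5 = 2.0, and 0.64 SD would be 1.3 points. The figure should be given as about 1.1 using the baseline SD. The gap to 1.9 remains.

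**Conclusion.** The concern holds. The NPRS conversion is wrong as written, and the clinical-relevance statement drawn from it is unsupported. The correct value is about 1.1 points, on the assumption that the plan's baseline SD of 1.7 applies. Larger assumed SDs of 2.0 to 2.5 leave it below the stated figure. The randomisation, the models, the alpha level and the planned n are unaffected. It should be corrected before the plan is relied on, because it is the sole relevance argument for a primary outcome and it feeds the closing statement that 0.64 SD is the minimally relevant effect.

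**What to change.** 1. In the Sample size justification, replace the conversion with 0.64 x 1.7 = 1.1 NPRS points, and say that it uses the baseline SD.
2. Delete the sentence that claims clinical relevance, or restate it for 1.1 points with support. Bring the closing statement on the minimally relevant effect into line for pain. If 1.9 points was the intended target, say so and re-derive the effect size, since it corresponds to 1.12 SD at an SD of 1.7.
3. As a separate improvement, pre-specify the between-group NPRS difference in points against which the confidence interval will be interpreted.

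The first two steps cost one figure and a sentence or two, and need no change in n if 0.64 SD is kept. The stated figure becomes less favourable. The third step costs somewhat more, because a value has to be chosen and supported, and the core correction does not depend on it.

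### The 0.64 SD between-arm target is supported by before-after changes with no comparator subtracted, and its clinical-relevance basis does not hold as written

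*Combined protocol and SAP*

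**What the plan says.** The opening design overview sets the contrast: "The primary comparison will consist of the combination group compared against each single treatment group of SMT or DN". Sample size justification sizes the trial on a standardized difference between two groups ("that is, a 0.64 SD difference"), "to achieve 80% power using a two-sided alpha 0.05 comparison". Statistical methods adds: "All comparisons will be made at the alpha 0.05 level".

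The support for 0.64 comes from two earlier studies. The passage beginning "In a DN study, baseline ODI was mean" takes ODI from 31.5 (SD 11.5) to 23.4 (SD 13.5), one week after DN, and divides the change by 12.6. The SMT figures go from 32.2 (SD 11.9) to 23.9 (SD 11.4), divided by 11.7, giving 0.71. The plan concludes: "So, both DN and SMT achieve a 0.64 SD effect size by themselves".

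It then acknowledges that the trial asks a different question, namely whether the combination beats each single treatment. It bridges the gap by suggesting that individual response may vary, "with some level of synergy of DN+SMT being more effective than the sum of the individual effects". It closes by adopting the 0.64 "SD effect size for this test as our minimally clinically relevant effect, consistent with the individual treatment effects".

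The section also offers a second basis. The planned size is said to work if 0.64 SD is either likely or at least a minimal clinically meaningful difference, and an NPRS calculation giving 1.9 points is put forward for the latter.

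**The concern.** A before-after change in one treated group is not the effect of the treatment. It can also contain natural course, regression to the mean and non-specific response to care. The plan subtracts no comparator change and does not mention these components. In a randomized between-arm contrast they are common to both arms and cancel. What remains is the increment from the added modality, and a within-group change in one modality does not estimate that.

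The target difference decides what a negative result means. If 0.64 SD is presented as what one modality already delivers, a non-significant contrast invites the reading that the second modality adds nothing, although a smaller increment could easily have been missed. The plan gives no rule for reading a non-significant result.

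**Working it through.** **Inputs**, all from Sample size justification: target 0.64 SD; two-sided alpha 0.05; 80% power; r = 0.50; ANCOVA factor 1 − r² = 0.75; retention 92%; the ODI means and SDs given above; NPRS baseline 5.0 (SD 1.7).

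**1. The plan's sample size.** A two-sample t test at 0.64 SD needs 39.3, so 40 per group (the text gives 41, then 40). Then 40 × 0.75 = 30, and 30/0.92 = 32.6, so 33 per group and 99 in total. The planned total reproduces.

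**2. What 0.64 and 0.71 are.** The SD of a one-group change is √(s₁² + s₂² − 2·r·s₁·s₂).
- DN: √(11.5² + 13.5² − 2 × 0.50 × 11.5 × 13.5) = 12.62; 8.1/12.62 = 0.64.
- SMT: √(11.9² + 11.4² − 2 × 0.50 × 11.9 × 11.4) = 11.66; 8.3/11.66 = 0.71.

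Both reproduce as standardized within-group changes, with no comparator term. The choice of divisor matters little at r = 0.50: for DN the pooled SD is 12.54 against 12.62.

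**3. What the target asks of the combination arm.** 0.64 × 12.6 = 8.1 ODI points between arms. If the single arm repeats the DN figures and ends at 23.4, the combination must end at 23.4 − 8.1 = 15.3. That is a fall of 31.5 − 15.3 = 16.2 points, or 51% of baseline, twice the single-arm change.

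**4. The NPRS argument.** The plan computes (5.0/1.7) × 0.64 = 1.9. That divides the mean by the SD and does not convert SD units to points. The conversion is 0.64 × 1.7 = 1.09 points. A change of 1.9 points would be 1.9/1.7 = 1.12 SD.

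**5. Power at smaller differences.** Two-sample t test, 30 evaluable per arm, residual SD √0.75 = 0.866. The last column repeats the plan's own chain (t test, × 0.75, ÷ 0.92, × 3 arms). The documents do not say how much of the 0.64 is non-specific. The smaller rows assume a share of 25% or 50%, with the added modality contributing the rest in full.

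| Assumed share | Difference (SD) | ODI points (× 12.6) | Power per contrast | Total N for 80% |
|---|---|---|---|---|
| 0% | 0.64 | 8.1 | 80% | 99 |
| 25% | 0.48 | 6.0 | 56% | 174 |
| 50% | 0.32 | 4.0 | 29% | 384 |

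**6. Precision.** SE = √(2 × 0.75/30) = 0.224 SD, so a 95% CI extends about ±0.45 SD. An observed difference of 0.64 SD would give about 0.19 to 1.09.

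**The case against.** The strongest defence is that the trial is sized on a minimally relevant difference, and such a trial need not be powered for anything smaller. The principle is right, and the plan does state this basis. It does not rescue the target as written: no minimal important ODI difference is given, the only worked support is the NPRS figure that fails in step 4, and the closing sentence ties the target back to the single-treatment changes.

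Other parts of the defence stand and limit the point.
- A reader might infer that the two source studies were uncontrolled. The documents do not say; they show only that the figures used are within-group changes.
- A reader might infer that the claim about DN and SMT is false. The documents show only that it is unsupported, since they do not give the non-specific share.
- A reader might count the shared exercise programme among the parts that cancel. The sample size is for week 2. Home exercise is assigned after the fourth session, and patient-reported outcomes are taken 48 hours after that session. Shared exercise is therefore nearly absent from the powered contrast.
- A reader might infer that the plan means to test synergy, or to report within-arm change as efficacy. It specifies neither. Synergy is offered to make the target plausible, and the models in Statistical methods compare arms.

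**Conclusion.** The concern holds in a limited form. The arithmetic behind 0.64, 0.71 and N = 99 reproduces; the fault lies in what the numbers are said to show. Within-group changes are labelled as effects of DN and SMT and reused as the expected advantage of the combination over an active single treatment. The documents establish neither. The fallback to minimal clinical relevance lacks an ODI reference value and rests on an NPRS conversion that should read 1.09 points, not 1.9.

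The 8.1-point and 16.2-point figures follow directly from the plan's numbers. The 56% and 29% power figures are illustrations that depend on an assumed non-specific share, full contribution of the added modality, r = 0.50 and 30 evaluable per arm. It would go too far to conclude that the trial is underpowered for the true effect or that 99 is the wrong number, because the documents contain no estimate of the true increment.

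**What to change.** Revise Sample size justification, keeping N at 99.

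1. Delete the sentence "So, both DN and SMT achieve a 0.64 SD effect size by themselves" and the closing clause that ties the target to the individual treatment effects. Present synergy only as an assumption.
2. State 0.64 SD (about 8 ODI points, 1.1 NPRS points) as an assumed between-arm difference. Say openly that the value came numerically from before-after changes. Justify it, if possible, against a between-group minimal important difference. Correct the NPRS conversion.
3. Report power at smaller differences beside it: 80% at 0.64, 56% at 0.48 and 29% at 0.32 SD, for 30 evaluable per arm and r = 0.50, with the smaller values marked as illustrative.
4. In Statistical methods, base conclusions on the two between-arm differences with 95% CIs. Treat a non-significant result whose CI still includes the stated minimal important difference as inconclusive, not as evidence of no added benefit. Restrict this rule to non-significant results: a rule based only on which values the CI covers could label the 0.19 to 1.09 interval in step 6 inconclusive, although it excludes zero.

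The cost is wording only; arms, outcomes, model and sample size do not change. The downside is that the stated justification and power look less favourable.
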